1.1 Protocol Amendment: Summary of Changes

Previous Protocol Versions

Protocol	Date
Original	10 February 2017
Amendment 1	03 March 2017
Amendment 1.01 (VHP Countries)	20 June 2017
Amendment 2	30 June 2017
Administrative Change 1	27 October 2017
Administrative Change 2	13 December 2017
Amendment 3	22 March 2018
Administrative Change 3	04 April 2018
Administrative Change 4	04 June 2018
Administrative Change 5	31 October 2018
Administrative Change 6 [Hong Kong (China) Only]	11 April 2019
Amendment 4	11 October 2019
Amendment 5	11 December 2019
Amendment 6	15 May 2020
Administrative Change 7	22 June 2020
Administrative Change 8	13 August 2020
Amendment 6.01 (Japan Only)	19 November 2020
Amendment 7 (all countries except Japan)	30 January 2021
Administrative Change 11 (China Only)	20 October 2022

The purpose of this amendment is to:

• Apply administrative changes throughout protocol.

Rationale: Revised text to improve consistency and readability, and/or provide clarifications.

• This includes the application of Administrative Change 11 throughout protocol.

Rationale: To reinstate the use of subject paper diary cards for sites in China only.

- Update the Title page to include the sponsor statement for the European Union. *Rationale:* The changes align with the sponsor's protocol template.
- Update Section 3.2 Benefits and Risks to include information on the ORAL Surveillance study, a study of a different JAK inhibitor.

Rationale: Additional detail provided based on the ORAL Surveillance study to support the current research.

• Update Section 3.2 Benefits and Risks to include a benefit:risk statement on the effects of upadacitinib on the course of COVID-19.

Rationale: To include detail for COVID-19.

• Update Section 5.1 Overall Study Design and Plan: Description, Follow-Up Period to add that the 30-day follow-up visit is allowed to be a phone call.

Rationale: Updated to align with discontinuation procedures and allow more flexibility in case there are no safety issues necessitating an in-person visit.

• Update Section 5.1 Overall Study Design and Plan: Description, Follow-Up Period and Section 5.4.1 Discontinuation of Individual Subjects to add that follow-up visit/phone call is not applicable to subjects who begin commercially available upadacitinib or adalimumab.

Rationale: Updated to latest AbbVie standards.

[figure not shown]

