5.0 Investigational Plan

5.1 Overall Study Design and Plan: Description

This is a Phase 3 multicenter study that includes two periods. Period 1 is 56 weeks in duration and includes a 24-week randomized, double-blind, parallel-group, placebo-

[figure not shown]
controlled and active comparator-controlled period followed by an additional 32 weeks of blinded, active comparator-controlled treatment (Weeks 24 – 56). Period 1 is designed to compare the safety, tolerability, and efficacy of upadacitinib 15 mg QD and 30 mg QD versus placebo and versus adalimumab 40 mg eow for the treatment of signs and symptoms of subjects with moderately to severely active PsA and have an inadequate response or intolerance to non-biologic DMARDs (DMARD-IR). Period 1 is also designed to compare the efficacy of upadacitinib 15 mg QD and 30 mg QD versus placebo for the prevention of structural progression. Period 2 is an open-label (blinded until the last subject completes the last visit of Period 1), long-term extension of up to a total treatment duration of approximately 5 years to evaluate the safety, tolerability and efficacy of upadacitinib 15 mg QD and 30 mg QD in subjects with PsA who have completed Period 1.

Upon approval of protocol amendment 7, subjects receiving upadacitinib 30 mg QD will be switched to upadacitinib 15 mg QD at their next scheduled study visit.

The study is designed to enroll approximately 1640 subjects at approximately 350 study centers worldwide to meet scientific and regulatory objectives without enrolling an undue number of subjects in alignment with ethical considerations.

The study duration will include a 35-day screening period; a 56-week blinded period which includes 24 weeks of double-blind, placebo-controlled and active comparator-controlled treatment followed by 32 weeks of active comparator controlled treatment (Period 1); a long-term extension period of up to a total treatment duration of approximately 5 years ([blinded until the last subject completes the last visit of Period 1] Period 2); a 30-day follow-up call or visit; and a 70-day follow-up call.

Subjects who meet eligibility criteria will be stratified by extent of psoriasis (\geq 3% body surface area [BSA] or < 3% BSA), current use of at least 1 DMARD, presence of dactylitis, and presence of enthesitis, except for subjects from China and Japan, where randomization for each country will be stratified by extent of psoriasis (\geq 3% body

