8.0 Study Drug Exposure and Compliance

8.1 Study Drug Exposure

For short term up to Week 24, the duration of exposure to study drug will be summarized for the safety analysis set by the randomized treatment groups.

For long term, the duration of exposure to study drug will be summarized for the safety analysis set by the following groups.

1. Upadacitinib 15 mg QD

This includes upadacitinib 15 mg QD exposure from subjects starting on upadacitinib 15 mg QD and subjects switching from placebo to upadacitinib 15 mg QD.

2. Upadacitinib 30 mg QD

This includes upadacitinib 30 mg QD exposure from subjects starting on upadacitinib 30 mg QD and subjects switching from placebo to upadacitinib 30 mg QD. Exposure is censored at time of dose switch from upadacitinib 30 mg QD to upadacitinib 15 mg QD.

3. Upadacitinib 15 mg QD switched from upadacitinib 30mg QD

This includes Upadacitinib 15 mg QD exposure from subjects who switched dose from upadacitinib 30 mg QD to upadacitinib 15 mg QD.

4. Adalimumab 40 mg EOW

Exposure to upadacitinib and placebo is defined as last dose date minus first dose date plus 1 day. Exposure to adalimumab is defined as last dose date minus first dose date plus 14 days.

Starting with Amendment 6.01 (for Japan) and Amendment 7 and 7.01(for global), subjects receiving upadacitinib 30 mg QD will be switched to receiving upadacitinib 15

mg QD. Exposure to upadacitinib 30 mg QD (Groups 2) will be censored prior to the day subject received the first dose of upadacitinib 15 mg QD, and subsequent exposure to upadacitinib 15 mg QD will be summarized under separate groups (Groups 3).

The duration of exposure to study drug will be summarized for each group as specified above, with the number of subjects, mean, standard deviation, median, minimum and maximum values. In addition, the number and percentage of subjects exposed to study drug will be summarized for the following cumulative duration intervals.

- ≥ 2 weeks
- ≥ 1 month
- \geq 3 months
- \geq 6 months
- ≥ 9 months
- ≥ 12 months
- ≥ 18 months
- ≥ 2 years
- ≥ 2.5 years
- ≥ 3 years
- ≥ 3.5 years
- \geq 4 years
- ≥ 4.5 years

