Treatment comparisons of upadacitinib versus ADA will be provided for key safety endpoints including overview of AE, overview of AESI, selected lab parameters, and potentially clinically significant laboratory values. Treatment difference and corresponding 95% CI will be provided.

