10.2.2 Analysis of Long-Term Adverse Event Rates

Long-term adverse events will be analyzed using event rates adjusted by cumulative exposure and will be based on the actual treatment received at the time of AE occurrence. For subjects switched from upadacitinib 30 mg QD to upadacitinib 15 mg QD, adverse events and exposure to upadacitinib 30 mg QD will be censored at the time of dose switch; subsequent adverse events and exposure starting the day of first dose of upadacitinib 15 mg QD will be summarized under separate groups. The detailed treatment groups including the handling of dose switch, are described in Section 8.1.

Exposure-Adjusted Event Rate (EAER)

To adjust for potentially different follow-up time between treatment groups, EAER will be provided. For the purpose of event rate calculation, the numerator will be the total number of AEs reported for the event (i.e., a subject can contribute more than one event to the numerator) and the denominator will be the total exposure time among subjects under the treatment group. The number of AEs reported (numerator), the total number of years of study drug exposure (denominator), and the exposure-adjusted AE event rate per 100 patient-years, calculated as ([numerator/denominator])*100, will be presented for each treatment group. The EAER will be the main approach to evaluate AEs in the long-term analysis.

The exposure adjusted incidence rate (censored at the time of first event) may be conducted for selected AESI endpoints as appropriate for long-term analysis.

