Appendix F. Statistical Analysis to Account for the Impact of COVID-19 Pandemic

This section presents the changes in statistical analysis to handle the missing data due to COVID-19 and the additional data collected related to COVID-19. The Week 24 primary database lock was completed in Jan 2020. The analyses specified in this section only applies to the long-term database lock.

Patient Disposition

Reasons for premature discontinuation of study drug/study will be updated to add two additional reasons related to COVID-19.

[figure not shown]
- COVID-19 Infection
- COVID-19 Logistical restrictions

The number and percentage of subjects who prematurely discontinued from study drug/study due to COVID-19 infection or COVID-19 logistical restrictions will be summarized by randomized treatment group.

Summary of COVID-19 Impacted Visits

Types of missing visits related to COVID-19 will be collected for the protocol prespecified visits. For each visit, the number and percentage of subjects impacted by COVID-19 will be summarized by the types of visit for each randomized treatment group as well as overall:

- In person, partial assessments done
- Virtual visit
- Missed visit

Efficacy Analyses

With respect to COVID-19 pandemic, it would be reasonable to assume that missed visits and missing data due to self-quarantine or local government restrictions on travel or limitations on healthcare resources will impact subjects across treatment arms in a similar fashion and adopt the Missing at Random (MAR) assumption for missing data handling.

As described in Section 9.3, longitudinal analysis models MMRM and GLMM, as well as NRI analysis for binary variables will be used for long term efficacy analysis for the treatment sequences, and will be maintained for long term efficacy analysis in the presence of missing data due to COVID-19.

Additionally, treatment comparisons between each upadacitinib dose versus adalimumab will be made for non-radiographic efficacy endpoints for the originally randomized upadacitinib groups and adalimumab group.

For radiographic related endpoints, the analysis will be based on linear extrapolation imputation (Week 24 and Week 56 analysis) and AO data. MMRM will be used for continuous radiographic endpoints for Week 104 and future analysis.

Safety Analyses

COVID-19 related AEs occurring on or after February 1, 2020 and COVID-19 related deaths occurring on or after February 1, 2020 will be collected.

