Listings of subjects with AEs related to COVID-19 infection will be provided.

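### At data cuts well after the dose switch, the crude long-term AE rates for upadacitinib 30 mg and adalimumab cover different calendar time, and COVID-19 events are counted without alignment or a COVID-excluded rate

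*SAP*

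**What the plan says.** On COVID-19 safety data, SAP Appendix F says that "COVID-19 related AEs occurring on or after February 1, 2020 and COVID-19 related deaths occurring on or after February 1, 2020 will be collected" and that "Listings of subjects with AEs related to COVID-19 infection will be provided". The rest of the appendix covers discontinuation reasons, affected visits and missing efficacy data.

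The main long-term AE measure (SAP 10.2.2) is the exposure-adjusted event rate (EAER): all events divided by all exposure, by treatment at the time of the event. For subjects who change dose, "adverse events and exposure to upadacitinib 30 mg QD will be censored at the time of dose switch". SAP 8.1 agrees: "Exposure to upadacitinib 30 mg QD (Groups 2) will be censored prior to the day subject received the first dose of upadacitinib 15 mg QD". Later time goes to a separate group: "This includes Upadacitinib 15 mg QD exposure from subjects who switched dose from upadacitinib 30 mg QD to upadacitinib 15 mg QD".

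The switch is set by protocol amendment. Protocol 5.1 places it at the first planned visit after approval: "Upon approval of protocol amendment 7, subjects receiving upadacitinib 30 mg QD will be switched to upadacitinib 15 mg QD at their next scheduled study". Protocol 1.1 dates Amendment 7 (all countries except Japan) "30 January 2021" and Amendment 6.01 (Japan) 19 November 2020. Adalimumab subjects may stay on treatment to Week 260 (Protocol 5.1.1), and the SAP sets no matching cut for them.

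SAP 10.1 adds: "Treatment comparisons of upadacitinib versus ADA will be provided for key safety endpoints including overview of AE". AESIs are included, and differences are given with 95% CIs. Serious infections are the serious subset of the company infections query (Table 11), and the overview counts every death (10.2.2.1). No rule sets COVID-19 events apart.

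**The concern.** Dividing by patient-years corrects for how long a group was followed, not for when. An event type that exists only from early 2020 adds to a group's overall rate in proportion to the share of its exposure after that date. The 30 mg group loses its late calendar time at the switch. Adalimumab and 15 mg keep theirs, and the 30-to-15 mg group has nothing else.

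SAP version 4.0 introduced both the COVID-19 handling and the dose-switch censoring, but does not connect them. At stake are the long-term overall AE, SAE, serious-infection and death comparisons of 30 mg with adalimumab, and how the switched group looks beside 30 mg in the same table.

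**Working it through.** The plan gives no figure on this point, so there is none to reproduce.

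**Inputs from the documents.** Group sizes are 410 (30 mg), 205 (placebo to 30 mg at Week 24) and 410 (adalimumab), with the same 410 + 205 structure for 15 mg. COVID-19 events count from 1 February 2020. Treatment lasts up to 260 weeks. The Week 24 lock was in January 2020, so enrolment ended by about mid-2019.

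**Assumptions, not in the documents.** Base case: uniform enrolment May 2017 to July 2019, switch in June 2021, 5% attrition per year, data to July 2024. Variations: enrolment from January 2018, switch in March or December 2021, 10% attrition, cut at mid-2022. COVID-19 risk is equal in all arms at any calendar time.

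**Formula.** Let b be the background rate and c the COVID-19 addition, both per 100 PY, and s the share of a group's exposure on or after 1 February 2020. The expected EAER is b + c × s. The artificial difference between two groups is c × (s₁ − s₂), so the background cancels.

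**Base-case exposure**

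| Group | PY | s |
|---|---|---|
| 30 mg, cut at switch | 1,594 | 0.458 |
| Adalimumab | 1,808 | 0.647 |
| 15 mg | 2,619 | 0.670 |
| 30-to-15 mg | about 1,025 (2,619 − 1,594) | 1.000 |

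Across the variations s is 39–53% for 30 mg and 55–72% for adalimumab.

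**Serious infections, b = 2, no true difference**
- c = 1: 30 mg 2 + 0.458 = 2.458; adalimumab 2 + 0.647 = 2.647. Difference −0.19, ratio 0.93.
- c = 2: 2.916 and 3.294. Difference −0.38, ratio 0.89.
- 30-to-15 mg against 30 mg: 3/2.458 = 1.22 and 4/2.916 = 1.37.
- 15 mg minus adalimumab: c × (0.670 − 0.647) = +0.02 to +0.05.

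**Sampling error.** SAP Appendix E gives a half-width of 1.96 × √(n₁/T₁² + n₂/T₂²). For c = 2, n₁ = 2.916 × 15.94 = 46.5 and n₂ = 3.294 × 18.08 = 59.6. The half-width is 1.96 × √(46.5/1594² + 59.6/1808²) = 0.0118 per PY, or about 1.2 per 100 PY.

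**Range at study end, c = 1 to 2.** With switches spread over several months, the ratio is about 0.87–0.95 and the difference −0.13 to −0.44, against half-widths of about 1.05–1.25. Placing every switch on one early or late day widens this slightly: 2.816/3.294 = 0.86 (s = 0.408, c = 2) and 2.534/2.647 = 0.96 (s = 0.534, c = 1). If the COVID-19 addition stops in 2022, the ratio is 0.93–0.97. With b = 3 and an addition rising from 1 to 3 after spring 2021, the rates are 3.53 and 4.45, a difference of about −0.9.

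**Mid-2021 cut.** With switches starting in March or September 2021, s is 43–54% for 30 mg and 45–51% for adalimumab, and the ratio is 0.99–1.02. If everyone switched on 1 March 2021, s is 0.41 and 0.46, and the ratio is 2.82/2.92 = 0.97.

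**After the fix.** Excluding COVID-19 events makes the artificial difference exactly 0 in this model. Censoring adalimumab at the corresponding switch date leaves +0.03 to +0.10 per 100 PY, because the placebo switchers began 30 mg 24 weeks later.

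**The case against.** Several arguments on the other side have weight.

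- **The events are visible.** A reader of Appendix F might infer that COVID-19 events appear only in a listing. That is not so: SAP 10.2.2.2 gives rates by treatment group for every SOC and PT, so a COVID-19 term would have its own row, and a COVID-free total could be approximated by subtraction. This stands. But subtraction does not correct the headline totals or supply a CI for the corrected difference.
- **The bias is not present at every cut.** SAP 4.0 serves Week 104 and later reporting. The last Week 104 visit falls around mid-2021, where the ratio is about 1.0 and its sign can reverse. This stands and limits the point to later cuts.
- **The effect is small against noise.** For serious infections it lies inside the CI at every rate tried. This stands, but the error is systematic and more follow-up does not remove it.
- **Other reporting may have fallen.** Appendix F expects missed and virtual visits, and fewer non-COVID reports in that period would offset the bias. The documents cannot settle this. It is a reason to align calendar time as well as exclude events.
- **Little rests on it.** A reader might infer that a dose conclusion depends on this comparison. The documents do not support that. The Week 24 data were locked in January 2020, Period 1 was reported under SAP 3.0, and 30 mg was already being replaced by 15 mg. No test of the 30-to-15 mg group against 30 mg is specified.

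**Conclusion.** The point holds for long-term cuts well after the switch and is a worthwhile improvement of moderate weight. The mechanism follows from the documents: crude rates, a cut for 30 mg only, a COVID-19 start date, and no alignment.

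The size rests on assumed enrolment, switch, attrition and COVID-19 rates. On those, the serious-infection ratio of 30 mg to adalimumab is about 0.87–0.95 at study end with no true difference, within sampling error, and about 1.0 at mid-2021. The direction, in favour of 30 mg, depends on equal COVID-19 risk across arms. The switched group would look worse than 30 mg (1.22 to 1.37 in the base case) without any dose effect. The 15 mg comparison with adalimumab is nearly balanced.

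It would go too far to conclude that COVID-excluded rates should become the main comparison. Protocol 3.2 says the effect of upadacitinib on the course of COVID-19 is not well defined, so exclusion alone could hide a real drug effect.

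**What to change.** In SAP 10.2.2 and Appendix F, keep the all-event EAERs and add the following for all AEs, SAEs, serious infections and deaths:

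1. The same EAERs and upadacitinib-minus-adalimumab differences with 95% CIs, excluding COVID-19-related events.
2. A calendar-aligned comparison: either rates split at 1 February 2020 and combined with common weights, or adalimumab events and exposure censored at the date corresponding to the 30 mg switch.

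Add a table note that the 30-to-15 mg group lies entirely after 1 February 2020 and should not be read directly against 30 mg.

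The flag for item 1 should already exist: Protocol 6.1.4, 6.1.7 and 10.2 require supplemental eCRFs for COVID-19-related events. The change needs SAP wording and repeat runs of planned tables. It needs no new data collection and does not alter the completed Week 24 or Period 1 reporting. The downside is a few more tables.
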